10.1 Description

The active study drug will be 20 mcg Spiropent tablets.

10.2 Treatment Regimen

Dosage will initially 40 mcg daily for one week, 40 mcg BID per oral daily for the next 5 weeks. If the 40 mcg BID per oral is well tolerated, the dose will be increased to 80 mcg each morning/40 mcg each evening for one week, followed by 80 mcg BID per oral for the remainder of the study.

10.3 Method for Assigning Subjects to Treatment Groups

All subjects will be assigned to the study drug.

10.4 Preparation and Administration of Study Drug

The drug will be stored and dispensed from the Investigational Drug Service at Duke University Health Systems ([contact]).

10.5 Subject Compliance Monitoring

Compliance (pill counts) will be measured at the Week 4, Week 12, and Week 24 visits. The subject will have phone visits during Week 1, 7, 12, 16 and 20, and compliance will be discussed then. Subjects who miss >6 doses of the study drug, will be considered non-compliant and withdrawn from the study ([Table 3](#)).

10.6 Prior and Concomitant Therapy

The use of the following concomitant meds is prohibited during the study:

- digoxin (digitalis, Lanoxin);
- diuretics (furosemide, Lasix);
- β -blockers such as atenolol (Tenormin), metoprolol (Lopressor), and propranolol (Inderal);
- tricyclic antidepressants such as amitriptyline (Elavil, Etrafon), doxepin (Sinequan), imipramine (Janimine, Tofranil), and nortriptyline (Pamelor);
- MAO inhibitors such as isocarboxazid (Marplan), phenelzine (Nardil), rasagiline (Azilect), selegiline (Eldepryl, Emsam), or tranlycypromine (Parnate); or
- other bronchodilators such as albuterol (Ventolin), levalbuterol (Xopenex), bitolterol (Tornalate), pirbuterol (Maxair), terbutaline (Brethine, Bricanyl), salmeterol (Serevent), isoetherine (Bronkometer), metaproterenol (Alupent, Metaprel), or isoproterenol (Isuprel Mistometer).

10.7 Packaging

The Investigational Drug Pharmacy at Duke will package drug for this study.

10.8 Blinding of Study Drug

Not applicable.

10.9 Receiving, Storage, Dispensing and Return

10.9.1 Receipt of Drug Supplies

Spiropent (PZN#01980325) will be purchased from Boehringer Ingelheim.

Upon receipt of the study treatment supplies, an inventory must be performed and a drug receipt log filled out and signed by the person accepting the shipment. It is important that the designated study staff counts and verifies that the shipment contains all the items noted in the shipment inventory. Any damaged or unusable study drug in a given shipment (active drug) will be documented in the study files. The investigator must notify study sponsor of any damaged or unusable study treatments that were supplied to the investigator's site.

10.9.2 Storage

Storage will be at ambient temperature in the Duke Hospital Pharmacy.

10.9.3 Dispensing of Study Drug

The Investigational Drug Service will dispense study drug (clenbuterol 20 mcg) to the study team at the Screening/Baseline/Week 0 visit. Subsequently, additional supply of study drug will be shipped before Week 18 to allow completion of the study. The Investigational Drug Service will maintain records of drug dispensing.

10.9.4 Return or Destruction of Study Drug

Unused drug will be destroyed by the Investigational Drug Service at the end of the study.

At the completion of the study, there will be a final reconciliation of drug shipped, drug consumed, and drug remaining. This reconciliation will be logged on the drug reconciliation form, signed and dated. Any discrepancies noted will be investigated, resolved, and documented prior to return or destruction of unused study drug. Drug destroyed on site will be documented in the study files.

11 Study Procedures

1. Research Activities: Medical History: Reviewed prior to study drug initiation.
2. Vital Signs: Completed at Screening/Baseline, Week 4, Week 12, and Week 24.
3. Physical Examination: Performed at Screening/Baseline, Week 4, Week 12, and Week 24.
4. AE Review: Completed at Week 4, Week 12, Week 24, and telephone visits.
5. Blood Samples: Blood samples will be obtained at Screening/Baseline, Week 4, Week 12, and Week 24. for the following analyses:
 - Safety Labs: Hematology and Chemistry (5 ml) to consist of:
 - a. Complete Blood Count (CBC)
 - b. Chemistry panel (including electrolytes, BUN, creatinine, glucose)
 - c. Liver panel (including albumin, aspartate aminotransferase (AST), alanine aminotransferase (ALT), and total bilirubin)
 - d. Creatine kinase (CK)
6. Electrocardiogram: Performed at Screening/Baseline, Week 4, Week 12, and Week 24.
7. Forced Vital Capacity (FVC) Testing: Performed at Screening/Baseline, Week 4, Week 12, and Week 24
8. ALSFRS-R: Performed at Screening/Baseline, Week 4, Week 12, Week 16, Week 20 and Week 24.
9. Muscle strength testing: Myometer testing (SORARU *et al.* 2006) and isometric muscle strength, and sub-maximum handgrip fatigue (SHEFNER *et al.* 2016), performed at Screening/Baseline, Week 4, Week 12, and Week 24.
10. Telephone visits: Performed during Week 1, 6, 16 and 20.
11. Serum pregnancy testing at Screening/Baseline. Urine pregnancy testing at Weeks 4, 12 and 24.
12. Thyroid function (T4, TSH) at Screening/Baseline.

Table 3: Testing Schedule

	Screening/ Baseline (Week 0)	Phone Visit (Week 1)	Study Visit (Week 4)	Phone Visit (Week 6)	Study Visit (Week 12)	Phone Visit (Week 16)	Phone Visit (Week 20)	Final Visit (Week 24)
Medical History	X							
Vital Signs	X		X		X			X
Physical Exam	X		X		X			X
Obtain Consent	X							
Study Drug Dispensed	X		X		X			
AE Review		X	X	X	X	X	X	X
Blood Sample	X				X			X
Safety testing	X		X		X			X
Thyroid function testing	X							
Pregnancy test								
Blood	X							
Urine			X		X			X
EKG	X		X		X			X
Pulmonary function testing	X		X		X			X
ALSFRS-R	X		X		X	X	X	X
Muscle strength testing	X		X		X			X

12 Statistical Plan

12.3 Subject Population(s) for Analysis

All subjects who complete the study will be included in the analysis, providing non-compliance is not documented.

13 Safety and Adverse Events

13.1 Definitions

13.1.1 Adverse Event

An *adverse event* (AE) is any symptom, sign, illness or experience that develops or worsens in severity during the course of the study. Intercurrent illnesses or injuries should be regarded as AEs. Abnormal results of diagnostic procedures are considered to be AEs if the abnormality:

- results in study withdrawal
- is associated with a serious AE
- is associated with clinical signs or symptoms
- leads to additional treatment or to further diagnostic tests
- is considered by the investigator to be of clinical significance

13.1.2 Serious Adverse Event

Adverse events are classified as serious or non-serious. A *serious adverse event* is any AE that is:

- fatal
- life-threatening
- requires or prolongs hospital stay
- results in persistent or significant disability or incapacity
- a congenital anomaly or birth defect
- an important medical event

Important medical events are those that may not be immediately life threatening, but are clearly of major clinical significance. They may jeopardize the subject, and may require intervention to prevent one of the other serious outcomes noted above. For example, drug overdose or abuse, a seizure that did not result in in-patient hospitalization, or intensive treatment of bronchospasm in an emergency department would typically be considered serious.

All AEs that do not meet any of the criteria for serious should be regarded as *non-serious adverse events*.

13.1.3 Adverse Event Reporting Period

The study period during which AEs must be reported is normally defined as the period from the initiation of any study procedures to the end of the study treatment follow-up. For this study, the study treatment follow-up is defined as 30 days following the last administration of study treatment.

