13.1.6 Post-study Adverse Event

All unresolved AEs should be followed by the investigator until the events are resolved, the subject is lost to follow-up, or the AE is otherwise explained. At the last scheduled visit, the investigator should instruct each subject to report any subsequent event(s) that the subject, or the subject's personal physician, believes might reasonably be related to participation in this study. The investigator should notify the study sponsor of any death or AE occurring at any time after a subject has discontinued or terminated study participation that may reasonably be related to this study. The sponsor should also be notified if the investigator should become aware of the development of cancer or of a congenital anomaly in a subsequently conceived offspring of a subject that has participated in this study.

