13.2 Recording of Adverse Events

At each contact with the subject, the investigator must seek information on AEs by specific questioning and, as appropriate, by examination. Information on all AEs should be recorded immediately in the source document, and also in the appropriate AE module of the case report form (CRF). All clearly related signs, symptoms, and abnormal diagnostic procedures results should be recorded in the source document, though should be grouped under one diagnosis.

All AEs occurring during the study period must be recorded. The clinical course of each event should be followed until resolution, stabilization, or until it has been determined that the study treatment or participation is not the cause. SAEs that are still ongoing at the end of the study period must be followed up to determine the final outcome. Any SAE that occurs after the study period and is considered to be possibly related to the study treatment or study participation should be recorded and reported immediately.

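### The AE reporting period runs to 30 days after the last dose, but nothing is scheduled after Week 24 and completers are asked to volunteer only events believed related

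*Combined protocol and SAP*

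**What the plan says.** Section 13.1.3 runs the AE reporting period from the first study procedure to the end of treatment follow-up, and sets that end: "For this study, the study treatment follow-up is defined as 30 days following the last administration of study treatment". Section 13.2 states the duty within the period, with no limit to related events: "All AEs occurring during the study period must be recorded". The definition in 13.1.1 is equally broad: "Intercurrent illnesses or injuries should be regarded as AEs".

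Section 13.2 also says how events are to be found: "At each contact with the subject, the investigator must seek information on AEs by specific questioning and, as appropriate, by examination". Section 11 (item 4) gives the schedule: "AE Review: Completed at Week 4, Week 12, Week 24, and telephone visits". Section 8.1 places the end of dosing and the final visit at Week 24, and the last AE review in Table 3 is in that column. The latest phone visit is at Week 20.

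For the time after the last visit, 13.1.6 makes two provisions for the subject. Open events are pursued: "All unresolved AEs should be followed by the investigator until the events are resolved". For new events, the text reads "At the last scheduled visit, the investigator should instruct each subject to report any subsequent event(s) that the subject", or that person's own doctor, "believes might reasonably be related to participation in this study". Section 9.4 adds a call and a follow-up visit, but only for those who withdraw early, and it gives no timing.

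**The concern.** The recording rule covers all AEs to day 198, while the procedure that finds them stops at day 168. For a completer with nothing ongoing at Week 24, a new event in the last 30 days reaches the study only if the subject volunteers it. The subject has been asked to do so only if they or their doctor suspect a link. Intercurrent illnesses and injuries count as AEs, and they are the events least likely to be seen as related.

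Safety is the primary endpoint (8.2) and AEs are summarised as frequencies (12.2), so the counts are the result. With 25 subjects, one missed subject is 1/25 = 4 percentage points. Serious events are exposed too. Section 13.3.1 sends all SAEs to the IRB and 13.6.1 sends them to the DSMB chair. Section 13.2 applies a relatedness limit to SAEs only after the study period. A hospital admission that the subject puts down to ALS need not be volunteered under 13.1.6.

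**Working it through.** **Inputs from the documents.** Last dose, final visit and last AE review at Week 24 (8.1, Section 11, Table 3); 30-day follow-up (13.1.3); 25 subjects (Section 5, 12.1); terminal half-life 34 hours (6.2).

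**Calendar**
- Last dose and last AE review: 24 × 7 = day 168.
- End of required reporting: 168 + 30 = day 198.
- Share of the period after first dose: 30/198 = 15.2%.
- Person-days if all 25 complete: 25 × 30 = 750 of 25 × 198 = 4,950, again 15.2%.

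**Scheduled AE reviews (Table 3)**
- To day 168: Weeks 1, 4, 6, 12, 16, 20 and 24, which is 7.
- Days 168 to 198: 0.

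**Residual drug in the window**
- Five half-lives: 5 × 34 h = 170 h = 7.1 days, leaving 0.5⁵ = 3.1%.
- 7.1/30 = 24% of the window carries residual drug; 30 − 7.1 = 22.9 days are essentially off drug.

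**Subjects who might be missed.** The documents give no AE rate, so both inputs here are assumptions. Let p be the probability that a completer has a new AE in the window, and c the fraction of such subjects whose event is self-reported as related. The expected number not captured is 25 × p × (1 − c).

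| p | Subjects with a new AE (25p) | c | Not captured |
|---|---|---|---|
| 0.05 | 1.25 | 0.75 | 1.25 × 0.25 = 0.31 |
| 0.10 | 2.5 | 0.50 | 2.5 × 0.50 = 1.25 |
| 0.20 | 5 | 0.25 | 5 × 0.75 = 3.75 |

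**Do the other provisions close the gap for a completer?**
- Pursuit of unresolved AEs (13.1.6): no, for a new event.
- Call and visit in 9.4: no, early withdrawals only.
- Questioning at each contact (13.2): no contact is scheduled.
- Week 24 instruction (13.1.6): only for events thought related. If its heading, which refers to post-study events, limits it to the time after day 198, it does not apply in the window at all.

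**The case against.** The strongest reply is that the recording duty in 13.2 still applies. The wording of 13.1.6 does not narrow it, so what is missing is a means of collection, and events are lost only if the site does no more than the visit table requires. Subjects come from the investigators' own clinic, and 13.2 requires questioning at any contact, so some events may surface in routine care. Related deaths and AEs, and possibly related SAEs after the study period, have their own reporting route. Most of the window is off drug and there is no control arm, so an unrelated illness then says little about safety at 80 mcg BID. Section 12.2 does not define the AE analysis window, so the effect on the reported tables is inferred.

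Much of this stands as a limit on size. Collection is passive rather than absent, the events most likely to be drug-related are the best covered, and the subject counts rest on assumed rates. The instruction in 13.1.6 is most naturally read as starting at Week 24, which is the reading kinder to the plan. None of it removes the mismatch. Clinic contact in the window is neither scheduled nor required, and the duty to record all AEs has no procedure behind it there. The one instruction given to completers asks for less than the rule.

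**Conclusion.** The concern holds. As written, the plan requires all AEs to be recorded to day 198, but from day 168 it gives completers only a self-report route limited to events thought related. The documented size is 30 of 198 days (15.2%) with 0 scheduled AE reviews, against 7 in the first 168 days. The likely loss is small: about 0.3 to 3.8 subjects of 25 if 5% to 20% have a new AE in the window and 25% to 75% of those report it as related. No rate in the documents supports or narrows that range. The effect on reported frequencies also assumes that the tables cover the full reporting period. There is no comparison arm or decision rule to distort. It should still be corrected, because it concerns primary-endpoint data, can include SAEs, and is cheap to put right.

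**What to change.** Add one AE review by phone about 30 days after the last dose (about day 198) to Section 11 and Table 3. In 13.1.6, have the Week 24 instruction ask subjects to report all AEs until that call, and keep the relatedness wording for events after it. This closes the 30-day stretch with no review.

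The cost is at most 25 short calls by existing staff, a last-subject-out date about 30 days later, and a few text edits. Dosing, sample size and efficacy analyses do not change. Rewording the Week 24 instruction costs nothing and is worth doing even if the call is not added.

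A separate editorial point, which carries no weight here: the phone weeks in 10.5 (1, 7, 12, 16, 20) differ from those in 8.1, Section 11 and Table 3 (1, 6, 16, 20). They should be aligned, after deciding whether the Week 7 call, which falls around the start of 80 mcg BID, is intended.

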13.1.4 Preexisting Condition

A preexisting condition is one that is present at the start of the study. A preexisting condition should be recorded as an AE if the frequency, intensity, or the character of the condition worsens during the study period.

13.1.5 General Physical Examination Findings

At screening, any clinically significant abnormality should be recorded as a preexisting condition. At the end of the study, any new clinically significant findings/abnormalities that meet the definition of an AE must also be recorded and documented as an AE.

13.1.6 Post-study Adverse Event

All unresolved AEs should be followed by the investigator until the events are resolved, the subject is lost to follow-up, or the AE is otherwise explained. At the last scheduled visit, the investigator should instruct each subject to report any subsequent event(s) that the subject, or the subject's personal physician, believes might reasonably be related to participation in this study. The investigator should notify the study sponsor of any death or AE occurring at any time after a subject has discontinued or terminated study participation that may reasonably be related to this study. The sponsor should also be notified if the investigator should become aware of the development of cancer or of a congenital anomaly in a subsequently conceived offspring of a subject that has participated in this study.

13.1.7 Abnormal Laboratory Values

A clinical laboratory abnormality should be documented as an AE if any one of the following conditions is met:

- The laboratory abnormality is not otherwise refuted by a repeat test to confirm the abnormality
- The abnormality suggests a disease and/or organ toxicity
- The abnormality is of a degree that requires active management; e.g. change of dose, discontinuation of the drug, more frequent follow-up assessments, further diagnostic investigation

13.1.8 Hospitalization, Prolonged Hospitalization or Surgery

Any AE that results in hospitalization or prolonged hospitalization should be documented and reported as a SAE unless specifically instructed otherwise in this protocol. Any condition responsible for surgery should be documented as an AE if the condition meets the criteria for an AE.

Neither the condition, hospitalization, prolonged hospitalization, nor surgery are reported as an AE in the following circumstances:

- Hospitalization or prolonged hospitalization for diagnostic or elective surgical procedures for a preexisting condition. Surgery should *not* be reported as an outcome of an AE if the purpose of the surgery was elective or diagnostic and the outcome was uneventful.
- Hospitalization or prolonged hospitalization required to allow efficacy measurement for the study.
- Hospitalization or prolonged hospitalization for therapy of the target disease of the study, unless it is a worsening or increase in frequency of hospital admissions as judged by the clinical investigator.

13.2 Recording of Adverse Events

At each contact with the subject, the investigator must seek information on AEs by specific questioning and, as appropriate, by examination. Information on all AEs should be recorded immediately in the source document, and also in the appropriate AE module of the case report form (CRF). All clearly related signs, symptoms, and abnormal diagnostic procedures results should be recorded in the source document, though should be grouped under one diagnosis.

All AEs occurring during the study period must be recorded. The clinical course of each event should be followed until resolution, stabilization, or until it has been determined that the study treatment or participation is not the cause. SAEs that are still ongoing at the end of the study period must be followed up to determine the final outcome. Any SAE that occurs after the study period and is considered to be possibly related to the study treatment or study participation should be recorded and reported immediately.

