6.1 Background

Amyotrophic lateral sclerosis (ALS) is a progressive neurodegenerative disease that lacks effective treatment, proceeding to respiratory failure and premature death for affected individuals. The neuropathy of ALS involves both upper motor neurons (UMN) and lower motor neurons (LMN) with critical secondary muscle involvement (KINSLEY AND SIDDIQUE 1993). UMN signs include hyperreflexia, Babinski sign, increased muscle tone, and weakness. LMN signs include weakness, muscle wasting, hyporeflexia, muscle cramps, and fasciculations. Affected individuals typically present with either asymmetric weakness of the extremities (stumbling or poor handgrip), termed “limb onset” or bulbar findings (dysarthria, dysphagia). Limb onset is more frequent than bulbar onset. Once it begins, the weakness progresses, ultimately leading to total disability and dependence and shortened survival. The mean age of onset is 56 years in individuals with no known family history and 46 years in individuals with more than one affected family member (familial ALS or FALS). Average disease duration is about three years, but it can vary significantly. Death usually results from compromise of the respiratory muscles. Multiple confirmed genetic and suspected environmental causes have been described (KINSLEY AND SIDDIQUE 1993). Current ALS treatments have little effect on disease progression and are mainly directed at optimizing quality of life (Oskarsson and Staff 2018).

The lack of effective therapy to reverse weakness or arrest ALS disease progression represents a critical unmet medical need. Clenbuterol’s ability to promote muscle hypertrophy and improve muscle function make it an attractive option for filling this need. Clenbuterol has been shown to stimulate muscle hypertrophy through inducing expression of insulin-like growth factor (Igf) -1 and Igf-2 and their receptors (MATSUMOTO *et al.* 2006).

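### No adverse event contact is scheduled after Week 24, although reporting runs to 30 days after the last dose, and 13.2 and 13.1.6 disagree on a non-serious event that is stable but unresolved

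*Combined protocol and SAP*

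**What the plan says.** Two sections of the combined protocol and SAP say when follow-up of an adverse event may end.

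- Section 13.2: each event is "followed until resolution, stabilization, or until it has been determined that the study treatment or participation is not the cause". For serious events it adds a stricter rule: "SAEs that are still ongoing at the end of the study period must be followed up to determine the final outcome".
- Section 13.1.6: unresolved events are followed "until the events are resolved, the subject is lost to follow-up, or the AE is otherwise explained".

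Section 13.1.3 sets the reporting period: "the study treatment follow-up is defined as 30 days following the last administration of study treatment".

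The assessment schedule is in Section 11: "AE Review: Completed at Week 4, Week 12, Week 24, and telephone visits". Table 3 places the telephone visits at Weeks 1, 6, 16 and 20. Under 8.1, subjects who tolerate the target dose stay on it until Week 24, which is also the final visit.

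Safety is the primary objective (Section 7) and the primary endpoint (8.2). Section 12.2 plans frequencies and distributions for adverse events, with no summary of outcome or reversibility.

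**The concern.** The trial has one arm, and some expected drug effects look like the disease. Section 6.1 states that "LMN signs include weakness, muscle wasting, hyporeflexia, muscle cramps, and fasciculations", and Table 1 reports cramps and fasciculations as adverse events in the earlier ALS study of clenbuterol. Background rates cannot be subtracted here. In the heart failure study in Table 1, two placebo subjects had cramps and two had tremor, and this trial has no placebo group to show the equivalent.

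What happens after the last dose therefore carries information. A drug effect should fade, while a sign of a progressive disease should not. If an event can be closed because it is stable on a constant dose, or because the investigator attributes it to ALS, and no one contacts the subject after dosing ends, that information need not be collected for the primary endpoint.

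**Working it through.** The plan gives no figure to reproduce. The check compares the text and adds one washout calculation.

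**Step 1. Compare the follow-up rules (non-serious events).**

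| Situation | 13.2 | 13.1.6 |
|---|---|---|
| Resolved | ends | ends |
| Stable, unresolved, unexplained | ends | continues |
| Judged to have another cause | ends | ends, if that counts as explained |
| Lost to follow-up | not listed | ends |

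The clear conflict is in the second row. The third row is close to agreement: a cramp attributed to ALS could be closed under either section. Serious events have their own rule in 13.2 and are not affected by the stabilization exit. Nothing in the plan says which section governs.

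**Step 2. Can an event be stable while still on drug?** Under 8.1 and 10.2 the dose rises at Week 6, with one intermediate week, and is then constant from Week 7 to Week 24 for subjects who tolerate it. That leaves 24 − 7 = 17 weeks at one dose. A persisting event can settle within that period and be closed under 13.2 before the drug stops.

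**Step 3. Compare the reporting window with the schedule.**

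- Reporting ends 30 days after the last dose (13.1.3).
- The last scheduled AE review is Week 24 (Section 11, Table 3).
- Completers take drug until Week 24 (8.1).
- Scheduled contacts between the last dose and day 30: none.

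Section 10.5 gives a slightly different list of phone weeks (1, 7, 12, 16 and 20), but that list also has nothing after Week 24.

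**Step 4. Is the existing window long enough to be useful?** The input is the 34-hour beta-phase half-life in 6.2.

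- Window: 30 × 24 = 720 h, and 720 / 34 = 21.2 half-lives.
- Five half-lives: 5 × 34 = 170 h, or 170 / 24 = 7.1 days.
- Fraction remaining at 7 days: 0.5^(168/34) = 0.033.
- Fraction remaining at 30 days: 0.5^(720/34) = 4 × 10⁻⁷.

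Day 30 is well past washout. The window is adequate, but no contact falls inside it.

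**Step 5. Does other text fill the gap?**

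- At the last visit, 13.1.6 has the investigator ask subjects to report later events they or their physician think may be related. That depends on the subject, and it concerns subsequent events rather than the status of ongoing ones.
- Section 9.4 has withdrawn subjects called and asked back for examination. It covers early withdrawals only and states no timing. Section 12.3 restricts the analysis to completers without documented non-compliance, so such data may not be analysed.

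**The case against.** The strongest reply is that little is lost. Section 13.2 states "All AEs occurring during the study period must be recorded", and it also requires AEs to be asked about at every contact. An event closed for follow-up therefore stays in the planned frequencies, and the subject is asked again at each contact through Week 24. Section 13.1.6 still asks for unresolved events to be followed. Cause can also be judged from onset relative to baseline and from timing relative to the staged dose increases. A day-30 call yields only self-report from someone who knows dosing has stopped. All of this stands, and it is why the point is minor.

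Several stronger readings are tempting, but the documents do not support them.

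- *That 13.1.6 demands follow-up to resolution without exception.* It also ends at loss to follow-up or when the event is otherwise explained, and the latter largely matches the not-the-cause exit in 13.2. Attribution ending follow-up is a weakness that both rules share, not a contradiction between them.
- *That events are dropped from the safety results.* They stay recorded and counted. Only their off-drug outcome may be missing.
- *That the loss can be sized from the heart failure study.* Its counts (cramps in 6 and tremor in 5 treated subjects) are of subjects who had the event at some time in 12 weeks, not of events ongoing at the last dose. Section 6.2 places side effects such as tremor at the start of treatment. No document gives a prevalence at Week 24.
- *That tremor is documented as overlapping with ALS.* Section 6.1 does not list it. The documented overlap is cramps and fasciculations.
- *That a phone contact would show whether a creatine kinase rise reversed.* That needs a blood test, so the proposal covers symptoms only.

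The reply does not answer the scheduling gap. Rewording 13.2 alone would create no off-drug observation, and 13.1.6 names no time at which one is made.

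**Conclusion.** The point holds, at minor severity. Sections 13.2 and 13.1.6 disagree on a non-serious event that is stable but unresolved, and must be reconciled. The main gap is that the 30-day reporting period contains no scheduled contact for completers, so off-drug status need not be collected for the primary safety endpoint.

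No AE count, test or sample size changes. The number of subjects affected cannot be derived from the documents. It lies between 0 and the 25 planned, depending on how many have an event ongoing at the last dose.

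The usefulness of a day-30 status rests on two assumptions: that symptoms caused by the drug fade as plasma levels fall, and that the 34-hour half-life in 6.2 applies to these subjects. With about 21 half-lives in the window, the conclusion is not sensitive to a moderately longer half-life.

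**What to change.** 1. **Reconcile 13.2 with 13.1.6.** State one list of follow-up end points for non-serious events, and say whether stabilization is among them.
2. **Add a phone AE contact about 30 days after the last dose** to Section 11 and Table 3, at least for subjects with an event ongoing at the last dose. Record status as resolved, improved, unchanged or worse, whatever the attribution and even if the event was stable on drug.
3. **Add one descriptive line to 12.2.** Among symptomatic events ongoing at the last dose, report the number and proportion resolved at that contact, by type of event. No test is needed. State that the status is unblinded self-report.

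The cost is one short call per such subject (25 at most), similar to the phone visits already planned, plus one small table. No new laboratory tests are involved. The limitation is that the status is self-reported by subjects who know they have stopped the drug, so the table is supportive evidence only.
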